Research Protocol Proposal:

Title: A Single Blinded Randomized Control Trial Comparing the Use of ARISTA Polysaccharide Hemostat in Total Knee Arthroplasty (TKA)

Version: August 13, 2020

NCT05522153

Investigators:

[name], DO FAOAO Chief of Orthopedics Virtua Burlington and Camden Campuses Burlington, NJ 08016

[name] Adult Reconstruction and Joint Replacement Service Hospital for Special Surgery New York, NY 10021

Purpose:

To determine if there is a benefit to overall reduction of blood loss, hematoma formation and outcomes in patients who undergo a primary unilateral TKA utilizing Arista MPH ® for hemostatic control.

Objectives:

The objectives of this study are to examine the effects of specific metrics in patients undergoing TKA with and without the utilization of Arista MPH® as a hemostatic adjunct.

These outcome metrics include direct comparison of:

- Blood loss (primary outcome)
- Transfusion rates (secondary outcome)
- Pre- and Post-operative thigh circumference
- Post-operative range of motion
- Adverse patient events within 90 days post-operatively

Number of Participants:

60 total patients (30 per group)

Methods:

Patients will be recruited from the Hospital for Special Surgery and Our Lady of Lourdes Programs. Patients will be prospectively enrolled when Institutional Review Board (IRB) approval is obtained. All patients will be undergoing a primary unilateral total knee arthroplasty for a diagnosis of osteoarthritis. Once enrolled in the study, each patient will be randomized into one of two groups. Group A will undergo a TKA utilizing Arista MPH ® intra-operatively. Group B will undergo a TKA without Arista MPH ®. All patients will receive a baseline IV dose of tranexamic acid per weight based guidelines prior to incision.

A thigh tourniquet will be utilized from prior to incision until wound closure is complete. Arista MPH ® will be used intra-operatively. A 5 gram vial of Arista MPH will be the standard of use. ARISTA will be used in accordance with the instructions for use. Additional need for Arista MPH ® usage during the case will be permitted and recorded. Standard electrocautory will be permitted, however additional thermal devices intended for hemostatic control will not be utilized.

Pre-operative hemoglobin, hematocrit, PT, PTT, and INR will be per standard institutional protocol within 30 days of surgery. The hemoglobin and hematocrit will be repeated 24 hours after the procedure per standard physician protocol. IV fluids administered pre-op, intra-op and post op for the first 24 hours will be recorded. Administration of any blood products from the time of incision until 90 days post-op will be recorded. Blood loss will be calculated via standard HSS. Drains will not be utilized.

The transfusion criteria is: a hemoglobin level of <8 g/dL or a hemoglobin level of <10 g/dL in a patient with symptomatic anemia or deemed at high risk because of notable underlying cardiac comorbidities. Blood will be administered 1 unit at a time, and the presence of symptoms or signs was reassessed.

Pre-operative thigh circumference will be measured on the day of the surgery. For standardization, the circumference will be recorded 15 cm proximal to the superior pole of the patella. Post-operatively the thigh circumference will be measured at 24 hours, post-operative day 14 +/- 4 days, and post operatively at 3 months +/- 1 week.

Post-operative knee range of motion will be recorded at 24 hours, post-operative day 14 +/- 4 days, and post-operatively at 3 months +/- 1 week.

Pre-operative and post-operative day 14 (+/- 4 days) and post-operative 3 months (+/- 1 week) knee society short form scores will be collected

All post-operative adverse events related to the procedure will be recorded. These invents include, but are not limited to: readmission, infection, prosthesis loosening, wound dehiscence, and wound drainage.

All data will be de-identified and securely maintained in an IRB approved manner.

Inclusion/Exclusion Criteria

Patients will be included if:

- They willingly desire to participate and signed the informed consent
- Are between the ages of 18 and 100 years of age
- Have the mental capacity to provide consent
- Are undergoing a primary unilateral total knee arthroplasty

Patients will be excluded from the study if any of the following exist:

- allergy to Arista MPH®
- allergy to tranexamic acid
- preoperative hepatic or renal dysfunction
- · serious cardiac or respiratory disease including coronary artery stent placement
- congenital or acquired coagulopathy as evidence by INR > 1.4 or PTT > 1.4 times normal
- thrombocytopenia as identified by a preoperative platelet count of < 150,000/mm3
- history of thromboembolic disease
- pregnant or breast feeding
- donated preoperative autologous blood
- diagnosis of inflammatory arthritis
- a preoperative hemoglobin < 10 g/dL.

Study Results

TABLE 1: DEMOGRAPHIC DATA (ALL PATIENTS OVER COURSE OF STUDY)

Number of Subjects Screened	
Number of Patients Enrolled:	
Age	Average \pm SD (Range)
Gender	Male:Female
Number of Withdrawn:	

Table 2: (ALL PATIENTS IN STUDY)

	PreOp	IntraOp	6Hrs
IV Fluids	Y/N	Y/N	Y/N
Hemoglobin	Average ± SD (Range)		Average ± SD (Range)

Hematocrit	Average ± SD (Range)		Average ± SD (Range)
Thigh circumference	Average ± SD (Range)		Average ± SD (Range)
KSS	Average ± SD (Range)		•
PT	Average ± SD (Range)		
PTT	Average ± SD (Range)		
INR	Average ± SD (Range)		
Blood products administered?		Y/N (count)	Y/N (count)
Adverse Events		Y/N (count)	Y/N (count)

Table 5: Additional data elements for all patients in study.

	24hrs	48hrs	28 days	90days
IV Fluids	Y/N			
Hemoglobin	Average ± SD (Range)			
Hematocrit	Average ± SD (Range)			
Thigh Circumference	Average ± SD (Range)	Average ± SD (Range)		
Blood products administered?	Y/N (count)	Y/N (count)	Y/N (count)	Y/N (count)
Adverse Events	Y/N (count)	Y/N (count)	Y/N (count)	Y/N (count)

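### Does a pre-operative hemoglobin up to 30 days old, with IV fluid tabulated only as yes/no, undermine the primary blood-loss outcome?

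*Protocol*

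**What the plan says.** Blood loss is the primary outcome (Protocol, Objectives). Its derivation is one sentence in Methods: "Blood loss will be calculated via standard HSS". No formula or list of inputs is given.

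On laboratory values, Methods says "Pre-operative hemoglobin, hematocrit, PT, PTT, and INR will be per standard institutional protocol within 30 days of surgery" and then "The hemoglobin and hematocrit will be repeated 24 hours after the procedure per standard physician protocol". On fluids it says "IV fluids administered pre-op, intra-op and post op for the first 24 hours will be recorded", without a unit. Two further statements bear on how blood loss could be measured: "Drains will not be utilized" and "A thigh tourniquet will be utilized from prior to incision until wound closure is complete". A study measurement on the day of surgery is already planned: "Pre-operative thigh circumference will be measured on the day of the surgery".

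Under Study Results, Table 2 has columns PreOp, IntraOp and 6Hrs, with mean, SD and range for hemoglobin and hematocrit at PreOp and 6Hrs. Table 5 has the same summaries at 24 hours. The four filled IV fluid cells in these tables are all Y/N. The sample size is "60 total patients (30 per group".

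**The concern.** With no drains and a tourniquet in place until closure, much of the loss would escape intra-operative collection, so a calculation from the fall in hemoglobin is a plausible reading of the blood-loss sentence. On that reading three things look weak.

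- **Baseline.** The pre-operative value may be up to 30 days old. A change in hemoglobin over that interval would be counted as surgical loss or as a gain.
- **Fluids.** IV fluid dilutes the post-operative value, and a Y/N entry cannot show by how much.
- **Sampling time.** The text schedules one post-operative sample, at 24 hours. Table 2 adds one at 6 hours, and neither is tied to the outcome.

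At stake is precision in a trial of 60 patients. A later analysis plan can name a formula or choose between two samples. It cannot supply a blood count that was never drawn or a volume that was never written down.

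**Working it through.** **The plan's own figure.** The 60 patients cannot be reproduced, because the document gives no significance level, power, effect size or SD with that number. What follows is sensitivity only.

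**Inputs.** From the protocol: 30 per group. Assumed: two-sided 5% test, blood volume 5,000 mL, hemoglobin falling from 13.5 to 11 g/dL, true between-patient SD of blood loss 300 mL. Pairs of results are for the fractional-drop formula, then the logarithmic one.

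**Without drift.** From the noncentral t distribution with 58 degrees of freedom, the difference detectable with 80% power is 0.7356 × 300 = 221 mL.

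**Sensitivity of calculated loss to baseline error.**
- Fractional, BV × (pre − post)/pre: 5000 × 11/13.5² = 302 mL per g/dL.
- Logarithmic, BV × ln(pre/post): 5000/13.5 = 370 mL per g/dL.

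**Effect of drift.** Error SD = sensitivity × drift SD, and total SD = √(300² + error SD²).

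| Drift SD (g/dL) | Error SD (mL) | Detectable difference (mL) | Power for 221 mL |
|---|---|---|---|
| 0.1 | 30 / 37 | 222 / 222 | 79.6% / 79.4% |
| 0.3 | 91 / 111 | 231 / 235 | 76.5% / 74.8% |
| 0.5 | 151 / 185 | 247 / 259 | 70.6% / 66.4% |
| 0.7 | 211 / 259 | 270 / 292 | 63.0% / 56.4% |

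**Drift needed for a 10% larger detectable difference.** This is true SD × √(1.1² − 1)/sensitivity: 300 × 0.458/302 = 0.46 and 300 × 0.458/370 = 0.37 g/dL. At true SD 200 mL it is 0.30 / 0.25 g/dL.

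**A second route, on the hemoglobin scale.** Assume the SD of the hemoglobin drop is 0.8 to 1.2 g/dL with a same-day baseline, and drift SD is 0.2 to 0.6 g/dL. The SD inflates by √(1.2² + 0.2²)/1.2 = 1.014 at one end and √(0.8² + 0.6²)/0.8 = 1.25 at the other. A design with 80% power falls to 79% or 61% (normal approximation). Both routes run from negligible to material, depending on an input that the document does not give.

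**Fluid.** Assume 24-hour volume has an SD of 0.5 to 1.0 L and 10% to 30% stays intravascular, so r = 50 to 300 mL. The added error SD is 5000 × (11 − 11 × 5000/(5000 + r))/13.5 = 40 to 231 mL (fractional), or 5000 × ln(1 + r/5000) = 50 to 291 mL (logarithmic). The detectable difference becomes 223 to 278 mL or 224 to 308 mL. Recording millilitres would not by itself remove this variance. Fluid given after randomization may respond to bleeding, so it belongs in a sensitivity analysis and not in the primary one. These figures are therefore not a gain that better recording would deliver.

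**A day-of-surgery draw has its own risk.** If 250 mL of fluid ran before the sample, with 10% to 30% retained, baseline hemoglobin would fall by 0.07 to 0.20 g/dL. Calculated loss would shift by 20 to 61 mL or 25 to 74 mL.

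**The tables against the text.** Tables 2 and 5 have no row for blood loss, which is the primary outcome, and none for range of motion, which the text schedules. The numbering jumps from 2 to 5, and Table 5 carries 48-hour and 28-day columns that are not among the visits in the text. They are report shells and do not list everything collected. The 24-hour hemoglobin and hematocrit in Table 5 agree with the text, so the 6Hrs column is one of several loose ends between tables and text.

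**The case for a change.** The best case for acting is that these are data-collection choices that nobody can repair afterwards, and that the remedy looks cheap: about 60 blood counts and a unit on the fluid fields. The same tables ask for a count of blood products but only Y/N for fluids, which suggests that volume was not intended. With 60 patients and no stated power, a loss from 80% to the low 60s, or lower, would hurt.

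Part of this stands. A stale baseline does add variance to any hemoglobin-based loss, and a sample nearer to surgery would be a reasonable optional refinement. The rest is weaker:

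- The pre-operative sentence groups hemoglobin with clotting tests that the exclusion criteria use, and nothing ties that sample to the calculation.
- Thirty days is a maximum and permits a sample the day before surgery.
- The exclusions for autologous donation, hemoglobin below 10 g/dL, coagulopathy, hepatic or renal dysfunction and inflammatory arthritis remove several reasons for hemoglobin to move before surgery.
- The calculation adds drift to an assumed true SD. An SD observed in patients with pre-admission baselines would already contain it.
- The existing samples follow standard practice. A mandatory extra draw would be a research procedure at two sites.

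**Conclusion.** No change to the plan is called for. The protocol is loosely worded here, but it contains no error that distorts the comparison. Both groups share the same baseline window and sampling schedule, so drift and similar dilution add noise and no bias.

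The noise matters only if the institutional method is hemoglobin-based, which the document does not say. Even then, at an assumed SD of 300 mL, drift must exceed an SD of about 0.46 (fractional) or 0.37 g/dL (logarithmic) before the detectable difference grows by more than 10%. Nothing in the document shows drift of that size. All these figures rest on assumed blood volume, hemoglobin levels and SDs.

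The formula, the sample that feeds it and the treatment of transfused units are details that the institutional method or an analysis plan can supply. The Y/N fluid cells stand in incomplete report shells, while the text says that fluids are recorded. The 6-hour column is a clerical mismatch with the 24-hour text, settled by wording when the tables are finalized.

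### Does the primary outcome need a new definition, given that blood loss is described only as the standard HSS calculation and one table shows a 6-hour hemoglobin that the Methods do not schedule?

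*Protocol*

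**What the plan says.** The Objectives list blood loss as the primary outcome. The Methods add one sentence on how it is obtained: "Blood loss will be calculated via standard HSS". No formula, unit, input list or source follows.

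The measurements that could feed such a calculation are in the Methods:

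- Pre-operative hemoglobin and hematocrit are taken within 30 days of surgery.
- After surgery, "The hemoglobin and hematocrit will be repeated 24 hours after the procedure per standard physician protocol".
- On fluids, "IV fluids administered pre-op, intra-op and post op for the first 24 hours will be recorded".
- On transfusion, "Administration of any blood products from the time of incision until 90 days post-op will be recorded".
- On what can be measured directly, "A thigh tourniquet will be utilized from prior to incision until wound closure is complete" and "Drains will not be utilized".

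On sites, "Patients will be recruited from the Hospital for Special Surgery and Our Lady of Lourdes Programs".

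In the Study Results shells, Table 2 has hemoglobin and hematocrit summaries under its pre-operative and 6-hour columns. Table 5 has them under 24 hours only. Neither table has a row for blood loss.

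**The concern.** A primary outcome should be reproducible from the plan. Here the reader is sent to the practice of an institution that is presumably one of the two recruiting programs, with nothing on what the other should compute.

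With the tourniquet on until closure and no drains, hemoglobin and hematocrit are the only listed measurements that could capture loss after tourniquet release. It is therefore reasonable to infer that the calculation uses them, although the protocol does not say so. On that inference, a 6-hour value in one table and a 24-hour value in the text look like two candidate primary results.

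If both were drawn and the more favorable one were reported, the type I error would exceed its nominal level. If the formula were also open, the reported difference in mL would depend on which formula was picked.

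**Working it through.** **1. Time points side by side.**

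| Source | Post-operative Hb/Hct |
|---|---|
| Methods | 24 h |
| Table 2 | 6 h |
| Table 5 | 24 h |

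The 24-hour sample is common to the text and a table. The 6-hour sample appears in one shell and nowhere in the schedule.

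**2. Is the 6-hour column specific to the primary outcome?** No. Table 2 also shows thigh circumference at 6 hours and Table 5 shows it at 48 hours, while the Methods set 24 hours, day 14 and 3 months. Table 5 has a 28-day column with no matching visit in the Methods. The numbering jumps from Table 2 to Table 5. The shells were evidently not aligned with the Methods in general. They are also headed as covering all patients, so they are not the by-arm outcome tables, and the lack of a blood-loss row in them says little.

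**3. What if the sample were chosen after seeing results?** Taking the better of two two-sided 5% tests with correlation ρ, the error is 1 − P(|Z₁| < 1.96, |Z₂| < 1.96), bivariate normal:

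| ρ (assumed) | Error |
|---|---|
| 0.5 | 9.1% |
| 0.7 | 8.3% |
| 0.9 | 7.0% |
| 0.95 | 6.5% |

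This needs three things that the protocol does not state: a hemoglobin-based formula, a 6-hour sample actually drawn, and a choice made on the results.

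**4. Does the hour of the sample move the comparison?** With blood volume 5 L and pre-operative hemoglobin 13.5 g/dL (both assumed), a 0.5 g/dL change between 6 and 24 hours moves one patient's calculated loss by 5000 × 0.5 / 13.5 = 185 mL. A shift common to both arms cancels in the difference between arms.

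**5. Does the formula move the conclusion?** Keep those assumptions and take arm means of 11.0 and 11.5 g/dL after surgery.

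- Fall divided by pre-operative value: 5000 × 2.5 / 13.5 = 926 mL and 5000 × 2.0 / 13.5 = 741 mL; difference 185 mL.
- Fall divided by the mean of pre- and post-operative values: 5000 × 2.5 / 12.25 = 1020 mL and 5000 × 2.0 / 12.5 = 800 mL; difference 220 mL.

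The second difference is 19% larger, but the spread grows with it. Per 1 g/dL of post-operative hemoglobin, the first formula changes by 5000 / 13.5 = 370 mL. Near 11.25 g/dL the second changes by 5000 × 2 × 27 / 24.75² = 441 mL. With an assumed SD of 1 g/dL the standardized differences are 185 / 370 = 0.50 and 220 / 441 = 0.50.

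Simulation with 30 per arm and 4,000 runs agrees: power was 47.6% and 47.3%, and the two formulas gave the same verdict on significance in 98% of runs. The choice is largely a rescaling.

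**The case for a change.** The strongest case for a change is that the definition of a primary endpoint belongs in the protocol, because its inputs must be collected from the first patient and a later SAP cannot recover what was never recorded. Formulas of this kind often use body size, and neither height nor weight is listed as a data element. The second program is not told explicitly to use the HSS method.

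Part of this stands: the protocol alone does not let an outside reader recompute the outcome. The rest is weaker.

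- The sentence is unqualified. It names one method for the trial and does not allow each site its own.
- Hemoglobin, hematocrit, fluids and blood products are all recorded. Weight must be known, because tranexamic acid is given by weight. That height is on the chart of an elective surgical patient is my assumption, but a safe one.
- If the programs did calculate differently, randomised patients in both arms would be affected alike. That could add noise, but it would not favor one arm.
- Whether the HSS method already allows for transfused red cells is unknown. The records needed to do so are planned.
- Yes/no cells for IV fluids in the shells do not show that volumes go uncollected.

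**Conclusion.** No change to the plan is called for. The wording is thin, but it names a method, and the Methods fix one post-operative sample, at 24 hours, which Table 5 confirms. Analysts would write out the named formula and use the scheduled sample. The SAP, which is not at hand, may already do so. No better method of measuring blood loss is at issue.

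The 6-hour column is a clerical mismatch in a reporting shell. It would matter only under the three unstated conditions in step 3, where the error would be 6.5% to 9.1% for correlations of 0.95 to 0.5. The documents give no sign of those conditions. The formula contrast of 185 against 220 mL leaves power essentially unchanged (47.6% against 47.3%).

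These figures assume a hemoglobin-based calculation, a 5 L blood volume, a fixed pre-operative hemoglobin of 13.5 g/dL and an SD of 1 g/dL, none of which the protocol supplies. They illustrate how little depends on the choice and are not estimates for this trial.

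### Range of motion is compared between groups after surgery, but no pre-operative measurement is scheduled, so there is no baseline to inspect or adjust for

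*Protocol*

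**What the plan says.** The Objectives list five outcomes for direct comparison between patients with and without the hemostat. Two of them are worded differently on timing: "Pre- and Post-operative thigh circumference" against "Post-operative range of motion". Blood loss is labelled primary and transfusion rate secondary; range of motion carries no label.

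The Methods follow that wording:

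- **Range of motion:** "Post-operative knee range of motion will be recorded at 24 hours, post-operative day 14 +/- 4 days", and at 3 months within one week. No pre-operative time point is given.
- **Thigh circumference:** "Pre-operative thigh circumference will be measured on the day of the surgery", then at 24 hours, day 14 and 3 months.
- **Knee society score:** "Pre-operative and post-operative day 14 (+/- 4 days) and post-operative 3 months (+/- 1 week) knee society short form scores" are to be collected.

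The trial has 60 patients, 30 per group, and "each patient will be randomized into one of two groups". The text shown mentions no stratification. It gives no SD for range of motion, no pre/post correlation and no detectable difference for this outcome.

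**The concern.** Range of motion before a knee replacement differs between patients, and a stiff knee may remain relatively stiff afterwards. If so, part of the post-operative spread is explained by where each patient started. A baseline measurement lets the analysis remove that part. It also lets a reader see whether the two groups started from the same place.

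With 30 per group, some chance imbalance in starting motion is to be expected. Without a baseline, nobody can tell whether an observed difference, or the lack of one, partly reflects it.

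This cannot be left to a statistical analysis plan. Choosing a covariate belongs there, but collecting it does not. Once the joint has been replaced, pre-operative motion can no longer be measured. A routine chart value may exist, but whether it does, and how it was taken, is unknown.

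**Working it through.** The protocol gives no power calculation for this outcome, so there is no stated figure to reproduce. The check asks what a scheduled baseline would be worth.

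**Input from the protocol:** 30 patients per group.

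**Assumptions, not in the protocol:** two-sided 5% level; 80% power; complete data on all 60 patients; equal SDs in the two groups; r (pre/post correlation) from 0 to 0.7; SD of motion 10, 15 or 20 degrees where degrees are needed.

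**Step 1. Post-operative values only.** The standard error of the group difference, in SD units, is √(2/30) = 0.258. With the noncentral t distribution on 58 degrees of freedom, 80% power is reached at a true difference of 0.736 SD.

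**Step 2. Baseline as covariate.** The variance is multiplied by (1 − r²) × (1 + 1/56), and 57 degrees of freedom remain. The second factor is the price of estimating the slope. At r = 0.5, for example, the factor is 0.75 × 1.018 = 0.763 and the standard error is 0.258 × √0.763 = 0.226 SD.

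| r | Detectable difference (SD) | Change from 0.736 | Power at 0.736 SD | Patients per group needed without a baseline for the same threshold |
|---|---|---|---|---|
| 0.1 | 0.739 | +0.4% | 80% | 29.8 |
| 0.2 | 0.727 | −1% | 81% | 30.7 |
| 0.3 | 0.708 | −4% | 83% | 32.3 |
| 0.5 | 0.643 | −13% | 89% | 39.0 |
| 0.7 | 0.530 | −28% | 97% | 56.8 |

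At r = 0 the covariate costs slightly more than it gives: 0.742 instead of 0.736 SD. Setting the adjusted threshold equal to 0.736 gives a break-even of r = 0.135. A 10% lower threshold needs r = 0.452.

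**Step 3. Chance imbalance at baseline.** The baseline difference between groups also has a standard error of 0.258 SD. By the normal distribution, an imbalance above 0.25 SD in either direction has a probability of about 33%, and one above 0.5 SD about 5%. In degrees, the 95% range is ±1.96 × SD × 0.258:

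- SD 10: ±5.1 degrees
- SD 15: ±7.6 degrees
- SD 20: ±10.1 degrees

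If the pre- and post-operative SDs are equal, r times this carries into the post-operative difference. At r = 0.5 that is 2.5, 3.8 or 5.1 degrees.

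**Step 4. Is this bias?** No. Over all randomizations the carry-over averages zero and is already part of the standard error in Step 1. In 100,000 simulated trials for each r from 0.1 to 0.7, the type I error was between 4.9% and 5.1%, with or without the covariate.

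**The case against.** The strongest reply is that nothing here is wrong. The objectives ask only for post-operative motion, and the methods deliver exactly that. A comparison of randomized groups on a post-operative value is valid, so preferring an adjusted one is a preference for efficiency. All of this stands, and it is why the point is not called a contradiction or a bias.

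The outcome is also low in the hierarchy, and the protocol sets no power target for it. That stands too and limits the weight of the point.

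The size is assumed. The range runs from a slight loss at r = 0.1 to a 28% lower threshold at r = 0.7, and at r = 0.3 the gain equals only about two patients per group. Soon after surgery the correlation may be weak, so the 24-hour comparison may gain nothing. The document therefore cannot show that precision is actually lost. The imbalance figures in degrees restate the small sample size and are not a separate harm.

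The pre-operative knee society score could serve as a covariate. It is at best an indirect stand-in for motion, so it softens the point without removing it.

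Finally, asking for the same method at baseline presumes a stated method. The text shown gives a measuring landmark for thigh circumference but no method for range of motion. That is a fair remark on the remedy and is taken up in the fix.

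The objection does not answer the balance of cost. The measurement is brief, its worst statistical consequence is negligible, and the chance to take it is lost at surgery.

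**Conclusion.** The point holds as an inexpensive improvement to consider. The protocol schedules no pre-operative range of motion, although it does so for two comparable measures. A chance imbalance in starting motion can therefore be neither seen directly nor adjusted for.

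The loss of precision is conditional: nil below about r = 0.13, small at r = 0.3, and in my judgement material from about r = 0.5, where 30 patients per group with a baseline do the work of 39 without. These figures rest on the assumed test level, power, complete data and range of r.

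The threshold of 0.74 SD itself comes from the sample size; the missing baseline only limits how far it could be lowered. Validity of the post-operative comparison is not in question, and conclusions on blood loss and transfusion are untouched.

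**What to change.** Add a pre-operative range of motion measurement on the day of surgery, at the contact where thigh circumference is already taken. State the measurement method once and apply it at every time point. Add the value to the pre-operative data fields, and use it as a covariate when post-operative motion is compared between groups. Model details can be left to the statistical analysis plan.

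The cost is one short, non-invasive measurement and one data field per patient. If pre- and post-operative motion prove uncorrelated, the analysis loses one degree of freedom, with the small effect on the threshold shown above.

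### The Methods record only post-operative, procedure-related adverse events, while the Objectives and the results tables call for adverse events without a relatedness limit

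*Protocol*

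**What the plan says.** The Objectives introduce the outcomes with "These outcome metrics include direct comparison of" and include "Adverse patient events within 90 days post-operatively". That item carries no condition on cause.

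The Methods contain one rule on adverse-event collection: "All post-operative adverse events related to the procedure will be recorded". An open list of examples follows: "These invents include, but are not limited to: readmission, infection, prosthesis loosening, wound dehiscence, and wound drainage". The rule gives no end of the recording window and does not say who decides that an event is related.

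The same part of the Methods words the blood-product rule more widely: "Administration of any blood products from the time of incision until 90 days post-op will be recorded".

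Under Study Results, the shells headed "Table 2: (ALL PATIENTS IN STUDY)" and "Table 5: Additional data elements for all patients in study" each have an adverse-event row asking for yes/no and a count. Table 2 asks for these at IntraOp and 6Hrs, and Table 5 at 24hrs, 48hrs, 28 days and 90days. No cell mentions relatedness.

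The title describes the study as "A Single Blinded Randomized Control Trial". The protocol does not say whether the blinding extends to whoever assesses adverse events.

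**The concern.** Adverse events are one of the outcomes named for comparison between the groups. The Methods sentence makes relatedness a condition for recording an event at all, when it could be an attribute noted after recording. If sites follow the sentence as written, the comparison depends on a judgement for which the protocol gives no assessor, no criteria and no blinding. The reference to the procedure is itself unclear. Both groups undergo knee arthroplasty, and the text does not say whether an event attributed to the hemostat counts as related to the procedure.

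Two consequences are possible. If the judgement is made alike in both groups, events are lost from a trial with only 30 patients per group. If it is made differently by group, it could create or hide a difference. Both are risks that follow from the wording; neither has been shown to occur.

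The sentence also covers post-operative events only. The hemostat is applied intra-operatively, so the period left out is the one in which the intervention is given.

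**Working it through.** The point is mainly one of text, and the plan gives no figure to reproduce.

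**Scope, side by side**

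| Feature | Methods rule | Objectives | Study Results, Tables 2 and 5 |
|---|---|---|---|
| Relatedness | Related to the procedure only | No limit | No limit |
| Intra-operative period | Not covered | Not covered | Covered (Table 2, IntraOp) |
| End of window | Not stated | 90 days | 90 days |

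1. *Relatedness.* The Methods rule is narrower than the Objectives and both tables. The open list does not change this: it refers back to the related events, so it widens the types of event but keeps the condition.
2. *Intra-operative period.* The Methods rule is narrower than Table 2 only, because the Objectives item is itself post-operative.
3. *End of window.* The Methods rule is silent here, not narrower.

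**Cell count.** Table 2 has 2 adverse-event cells and Table 5 has 4, so 2 + 4 = 6. One (IntraOp) lies outside a post-operative rule. The other 5 carry no relatedness limit.

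**Illustration of size.** None of the rates below comes from the protocol except n = 30 per group. Assume:
- a true share of patients with an event, p, of 0.10 to 0.30 in each group;
- a share of events judged related, r, of 0.60 to 0.90;
- k events per affected patient, judged independently.

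An affected patient goes unrecorded with probability (1 − r)^k.

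*Equal filtering:* patients unrecorded = 60 × p × (1 − r)^k.
- k = 1: from 60 × 0.10 × 0.1 = 0.6 to 60 × 0.30 × 0.4 = 7.2.
- k = 2: from 60 × 0.10 × 0.01 = 0.06 to 60 × 0.30 × 0.16 = 2.88.
- The expected difference between groups is zero.

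*Unequal filtering:* the share judged related is a = 0.9 in one group and b = 0.6 to 0.8 in the other. The spurious difference is p × [(1 − b)^k − (1 − a)^k].
- k = 1: from 0.10 × (0.2 − 0.1) = 1.0 point (0.3 patients of 30) to 0.30 × (0.4 − 0.1) = 9.0 points (2.7 patients).
- k = 2: from 0.10 × (0.04 − 0.01) = 0.3 points (0.09 patients) to 0.30 × (0.16 − 0.01) = 4.5 points (1.35 patients).

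*Scale of the extreme:* at k = 1 the recorded rates are 0.30 × 0.9 = 0.27 and 0.30 × 0.6 = 0.18. The standard error is √(0.27 × 0.73/30 + 0.18 × 0.82/30) = 0.107, and 0.09/0.107 = 0.84.

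**The case against.** The strongest reply is that a short label is being set against its definition. The Objectives item is a one-line heading, and the Methods sentence is the only place that says which events are collected. On that reading the tables simply report whatever the Methods record. The shells are loosely fitted in any case: they pool all patients, jump from Table 2 to Table 5, and use time points (6 hours, 48 hours, 28 days) that the Methods do not schedule. The examples include readmission with no cause attached, so the filter may be loose in practice. Adverse events are labelled neither primary nor secondary, the bias is hypothetical, and its assumed extreme is under one standard error. Recording every event is also not the only way to make the document consistent.

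Part of this stands. The tables alone are weak evidence of intended scope, the intra-operative gap is with Table 2 only, and the illustration does not show that bias will occur. How events are ordered in the analysis can be left to the SAP, which is not shown here.

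The reply does not remove the conflict. The Objectives item is unqualified without any help from the tables. The open list still refers back to related events. The IntraOp cell has no source under a post-operative rule, however loosely the shells were drawn up. What sites record is settled by the protocol, and an SAP cannot restore events that were never written down.

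**Conclusion.** The concern holds. The protocol gives two scopes for one compared outcome: the collection rule is narrower than the Objectives and both tables on relatedness, and narrower than Table 2 on the intra-operative period (1 of 6 cells). That conclusion rests on the text alone.

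The effect on results cannot be estimated from the document. The illustrative ranges depend wholly on the assumed event rates and shares judged related, and they become smaller when affected patients have more than one event. They indicate a modest risk to a comparison that is already imprecise at 30 per group. This should be fixed because it concerns a named comparison outcome, cannot be repaired once data are collected, and is cheap to correct. It does not touch the primary outcome.

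**What to change.** Reword the Methods sentence so that every adverse event from incision to 90 days is recorded in both groups, with relatedness held as a separate field. State who judges relatedness and whether the procedure includes use of the hemostat. Ideally that person is unaware of the group, though the correction does not depend on that. All events can then be compared between groups, with related events as a second comparison. This supplies the Objectives item and all six table cells; starting at incision goes beyond the Objectives and is there to fill the IntraOp cell.

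Narrowing the Objectives item and the table labels would also make the document consistent, but it would leave an undefined relatedness filter on a compared outcome.

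The cost is a change of protocol wording and some extra data entry for 60 patients, with no added visits or contacts. The extra entry should be slight, although its exact amount depends on how many unrelated events occur.
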